#### 13.8.11 Drug Levels and Pharmacokinetic Assessment

See Appendix B, Section 19.2. In Phase 2, only 6 subjects enrolled in Arm A (at Duke) will have PK samples drawn.

# **14 SAFETY MONITORING AND REPORTING**

The Principal Investigator is responsible for the identification and documentation of adverse events and serious adverse events, as defined below. The Principal Investigator will review and sign off on all adverse events and problems as they occur and will report them to the IRB in accordance with HRPP policies and to the Sponsor, BioMimetix JV, LLC. At each study visit, the Principal Investigator or designee must assess, through non-suggestive inquiries of the subject or evaluation of study assessments, whether an AE or SAE has occurred.

# 14.1 Adverse Events

An adverse event (AE) is any untoward medical occurrence in a study subject which does not necessarily have a causal relationship with this treatment. For this protocol, the definition of AE also includes worsening of any pre-existing medical condition. An AE can therefore be any unfavorable and unintended or worsening sign (including an abnormal laboratory finding), symptom, or disease that occurs in any subject enrolled in this clinical trial. It may or may not be related to use of the BMX-001. Abnormal laboratory findings without clinical significance (based on the Principal Investigator's judgment) should not be recorded as AEs. But laboratory value changes that require therapy or adjustment in prior therapy are considered adverse events.

From the time the subject signs the informed consent form through 30 days after completion of the final BMX-001 treatment (for subjects in Arm A, this will be 30 days after the last chemo/RT for subjects in Arm B), all AEs must be recorded in the subject medical record and adverse events case report form.

AEs will be assessed according to the CTCAE version 4.03. If CTCAE grading does not exist for an AE, the severity of the AE will be graded as mild (1), moderate (2), severe (3), life-threatening (4), or fatal (5).

Attribution of AEs will be indicated as follows:

- Definite: The AE is clearly related to the BMX-001
- Probably: The AE is likely related to the BMX-001
- Possible: The AE may be related to the BMX-001
- Unlikely: The AE is doubtfully related to the BMX-001
- Unrelated: The AE is clearly NOT related to the BMX-001

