b Will transition to 5-day TMZ dosed at 150-200 mg/m^2 po daily for the 1st 5 days in 28-day cycle (Adjuvant Phase). Study assessments for HRQoL Measurements, and Hair Loss Evaluation will be obtained approximately every 8 weeks (+/- 2 weeks) when a subject returns for a Standard of Care visit, until tumor progression, death, or patient comes off of study. Cognitive testing will also be completed every 8 weeks and at SOC visits; Cognitive testing will continue after tumor progression. CBC with differential will be obtained approximately on Days 21 or 28 of each 28-day cycle, and CMP will be obtained approximately on Day 21 of each 28-day cycle, or per the ordering physicians Standard of care practice, during the adjuvant phase, until the subject comes off the study. If subject is transitioned to metronomic temozolomide because of poor tolerance to 5-day temozolomide, then they will continue to be on study. Moreover, if Optune is used during the adjuvant phase, then they will continue to be on study. Adjuvant temozolomide can start up to 4 weeks after radiation therapy has completed.

c Starting at Loading dose day or Day -5 to 0, this will occur once every other week during weeks 1-8. This may be modified to meet standard of care scheduling for patient visits.

d Weekly CBCs and CMPs will begin at week 2 and continue through week 8. Platelet count is part of CBC with differential count.

e ECG will be done at screening for all subjects. For subjects in Arm A, ECG will also be obtained before the loading dose is administered (within 5 to 60 minutes before the dose), and at 60 (+/- 15 min) minutes after the loading dose. Pre-dose (within 5 to 60 minutes before the dose), and Post-dose ( 60 +/- 15 min) ECGs will also be collected at the Week 1 first maintenance dose and on either one of the BMX-001 injection days in Week 4.

f See Appendix B for timing of PK sampling, Day 8 and Day 36 only. Phase 1- all subjects, Phase 2- 6 subjects at Duke. g HRQoL measurements will be completed during Screening as a baseline and then approximately every 8 weeks when a subject returns for a Standard of Care visit during the Adjuvant Phase. These assessments should be completed prior to other study-related evaluations at study visits, if at all possible.

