#### 16.5.2.3 Secondary Objective #3 for Phase 2: Adverse Events

The phase 2 portion of this study has two adverse event endpoints: (1) The proportion of patients who experience any grade 3 or 4 adverse event during radiation and temozolomide treatment, and (2) The proportion of patients who experience a grade 3 or 4 adverse event that is definitely, possibly, or probably related to BMX-001 treatment during this same period. Adverse events occurring between baseline through 2 weeks after discontinuation of radiation will be the focus of these analyses.

Adverse Event Monitoring and Tabulations: Adverse events will be tabulated in a different manner for semi-annual reports to the DSMB-Plus / DSMB, the manuscript summarizing the results of this study, and the final report included within ClinicalTrials.gov.

*DSMB-Plus / DSMB Monitoring:* Two tabulations of adverse events occurring during concurrent chemoradiation will be generated for DSMB-Plus / DSMB review including one that includes all toxicities regardless of attribution, and another that includes only toxicities that are possibly, probably, and definitely related to BMX-001 treatment. For each of these tabulations, the maximum grade of each type of toxicity experienced by each patient will be summarized with frequency distributions within each treatment group. The period of observation that will be the focus of these tabulations will extend 2 weeks after termination of radiation treatment. Additional tabulations will summarize adverse events experienced during adjuvant treatment.

For the manuscript, similar summaries of adverse events will be generated.

For ClinicalTrials.gov, serious adverse events and other adverse events will be summarized separately. These tabulations will reflect the number of patients who experience each type of toxicity regardless of grade or attribution.

16.5.2.4 **Secondary Objective #4 for Phase 2: Progression-Free Survival** Progression-Free Survival (PFS) is defined as the time between initiation of protocol treatment and disease progression or death. If the patient remains alive without disease progression, then PFS will be censored at last follow-up. Analyses similar to those described for OS will be generated for PFS.

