11 SECONDARY OBJECTIVE: ADVERSE EVENTS (AE)

The third secondary objective is to assess the safety and tolerability of standard RT and TMZ in combination with BMX-001 compared to standard RT and TMZ alone in newly diagnosed HGG patients. The collection of adverse events was stopped 30 days after completion of chemoradiation treatment +/- BMX-001. Adverse events were coded by clinical center staff.

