19 DESCRIPTION OF TABLES FOR REPORTING

The following tables and figures will be produced, source data listings will be provided

Description	Population		
Summary of Subject Disposition	ITT, Safety, Treated		
Summary of Important Protocol Deviations*	Safety		
DEMOGRAPHICS			
Summary of Demographic Characteristics	ITT, Treated		
SAFETY DATA	1		
Summary of All AEs	Safety		
Summary of TEAEs	Safety		
Summary of BMX-001 Related TEAEs	Safety		
Summary of Baseline AEs	Safety		
Summary of all AEs	Safety		
Summary of SAEs/Deaths	Safety		
Narratives of SAEs	Safety		
Summary of Pre and Post dosing Vital Signs	Safety		
Listing of Abnormal ECG findings post BMX-001 treatment	Safety		
Summary of clinically significant:	Safety		
 Clinical Laboratory Evaluations Physical Examinations: Abnormal physical examination findings 	Safety		
PK*	PK		
OUTCOMES			
os	ITT, Treated		
PFS	ITT, Treated		
Thrombocytopenia	ITT, Treated		
Cognitive Testing	ITT, Treated		
HRQoLs	ITT, Treated		
OTHER			
Treatment Disposition: TMZ, RT, BMX-001	Safety		

Treatment Exposure: TMZ, RT, BMX-001	Safety
Concomitant Medications	Treated
Analysis Sets, including subjects excluded from analysis	All
List of Withdrawals	All

^{*=} BioMimetix will provide

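### Adverse event collection ends at different points in the two arms, so safety tables with no cut-off of their own compare unequal observation windows

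*Protocol*

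**What the plan says.** **End of collection.** Protocol 14.1 starts AE recording at consent and continues it "through 30 days after completion of the final BMX-001 treatment (for subjects in Arm A, this will be 30 days after the last chemo/RT for" Arm B patients. The sentence is awkward, but Table 4 footnote i states the split plainly: last BMX-001 for those who receive it, last chemo/RT for those who do not. The footnote gives 30 days as a minimum. SAP 11 reports that "The collection of adverse events was stopped 30 days after completion of chemoradiation treatment +/- BMX-001", which can be read the same way but does not say so.

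**Treatment after RT.** Protocol 13.3 gives Arm A 2 further weeks of BMX-001 after the six weeks of RT and TMZ, and Arm B 2 weeks without treatment. Protocol 9.1.5 has missed doses made up at the end and allows interruptions of up to 3 weeks.

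**Tables with a common window.** The two AE endpoints (Protocol 16.5.2.3, SAP 11.1), the TEAE table (SAP 11.2.1), the two main DSMB tabulations (Protocol 16.5.2.3) and the thrombocytopenia endpoints (Protocol 16.5.2.2, SAP 10.1) all end 2 weeks after RT in both arms.

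**Tables without one.** SAP 19 lists "Summary of All AEs" separately from the TEAE summary, and also lists a summary of SAEs and deaths. Neither has an end day. For ClinicalTrials.gov, "These tabulations will reflect the number of patients who experience each type of toxicity regardless of grade or attribution", again with no window. Protocol 16.5.2.3 adds, in its DSMB paragraph, that "Additional tabulations will summarize adverse events experienced during adjuvant treatment".

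**The concern.** A table that counts patients with at least one event depends on how long each patient is watched. If one arm is followed for about two weeks longer, it collects more events even when the drug does nothing.

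The extra time is also not neutral. It falls around the first adjuvant TMZ cycle, a treatment given in both arms at a higher daily dose than during RT. Protocol 14.1 counts a laboratory change as an AE when it requires or changes therapy, so a low count on an adjuvant blood test can enter these tables. Toxicity from a shared treatment could then look like an Arm A excess in the registry record, in the overall AE summary and in the adjuvant tabulation shown to the DSMB.

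**Working it through.** Day 0 is the start of RT.

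**Inputs.** BMX-001 runs 2 weeks beyond RT (Protocol 13.3). RT takes 30 to 33 fractions in under seven weeks (Protocol 9.1.8.1). For the adjuvant start, Table 4 footnote b says "Adjuvant temozolomide can start up to 4 weeks after radiation therapy has completed". The 2-week lower limit comes from Protocol 9.1.1, which is Phase 1 text; applying it to Phase 2 is an assumption. For adjuvant counts, footnote b says "CBC with differential will be obtained approximately on Days 21 or 28 of each 28-day cycle", or per local standard of care.

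**Plan's own figure.** One loading dose plus twice weekly for 8 weeks: 1 + 2 × 8 = 17 doses, as Protocol 9.1.5 states.

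**Close of collection, on schedule.** RT ends on day 42 and BMX-001 on day 56.
- Arm A: 56 + 30 = day 86.
- Arm B: 42 + 30 = day 72.
- Gap: 14 days; 86/72 = 1.19, or 19% longer from RT start.
- After the common cut at 42 + 14 = day 56: 86 − 56 = 30 days in Arm A and 72 − 56 = 16 in Arm B.

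**Range.** Taking RT end on days 40 to 47 and the last BMX-001 dose on days 53 to 56, the gap runs from (53 + 30) − (47 + 30) = 6 days to (56 + 30) − (40 + 30) = 16 days. With 3 weeks of made-up doses the last dose moves to day 77, Arm A closes on day 107, and the gap is 107 − 72 = 35 days.

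**Cycle-1 days captured.** Days = min(28, close − adjuvant start), with cycle day k falling k days after the start point.

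| Adjuvant start after RT | Start day | Arm A | Arm B | Arm A share | Day 21 falls on | Day 28 falls on |
|---|---|---|---|---|---|---|
| 2 weeks | 56 | 28 | 16 | 28/44 = 64% | 77 | 84 |
| 3 weeks | 63 | 23 | 9 | 23/32 = 72% | 84 | 91 |
| 4 weeks | 70 | 16 | 2 | 16/18 = 89% | 91 | 98 |

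In these three cases neither count falls inside Arm B's window (day 72). Arm A's window (day 86) contains Day 21 for a 2- or 3-week start, Day 28 for a 2-week start only, and neither for a 4-week start. Day 21 reaches Arm B's window only if adjuvant TMZ starts within 72 − 21 − 42 = 9 days of RT end.

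**Possible effect on counts (illustration).** Assume a constant event hazard from RT start and no drug effect. Arm A proportion by day 86 = 1 − (1 − p)^(86/72), where p is the Arm B proportion by day 72.
- p = 20% gives 23%.
- p = 30% gives 35%.
- p = 50% gives 56%.

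The documents give no hazard, so this shows scale only.

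**Early stoppers.** Read literally, an Arm A patient whose last dose is before day 42 closes before Arm B's day 72. A last dose on day 21 closes collection on day 51. A last dose before 56 − 30 = day 26 closes it before even the common cut on day 56.

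**The case against.** The strongest reply is that the results that matter most are protected. The AE endpoints, TEAE table, main DSMB tabulations and thrombocytopenia endpoints share an RT-anchored window. A reader might infer that the trial's formal safety comparison, or its marrow-protection claim, is biased by the longer Arm A follow-up. The documents do not support that: days later than 2 weeks after RT cannot enter those results. This stands in full.

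On the remaining tables, several limits also stand:
- SAP 19 is a list of titles and populations. SAP 11.2.2 heads the SAE summary as covering chemoradiation, without an end day, and the SAEs/Deaths table may simply be its output.
- The adjuvant tabulation is in the protocol only, and explicitly only for the DSMB; for the manuscript the protocol promises just similar summaries. The SAP lists no adjuvant AE table and takes precedence where methods differ substantially.
- The exposed tables are descriptive; no between-arm test is planned for them.
- Footnote i sets a minimum, so actual follow-up may be longer in either arm.
- Adjuvant counts are approximately timed. At a 2-week start, Day 21 misses Arm B's window by only 77 − 72 = 5 days.

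What the reply does not remove is that the all-AE summary and the registry tables are between-arm counts with no cut-off, fed by a collection rule that differs by arm. Following the plan as written gives unequal windows.

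**Conclusion.** The point holds for the tables that state no cut-off: the all-AE summary, the SAEs/Deaths summary unless it is limited to chemoradiation, the ClinicalTrials.gov SAE and other-AE tables, and the protocol's adjuvant tabulation. On schedule, Arm A is observed about 14 days longer (6 to 16 across planned schedules, about 35 with three weeks of made-up doses). Under the assumed 2- to 4-week adjuvant start, Arm A holds 64% to 89% of the captured cycle-1 days.

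Two stronger readings are tempting. One is that the bias always runs against BMX-001. Usually it will, but the literal rule closes collection sooner for Arm A patients who stop the drug early, and for them it reverses. The other is that cycle-1 marrow toxicity can be seen only in Arm A. Arm B still captures 2 to 16 days of the cycle, and with a 4-week start neither arm reaches the Day 21 count. The contrast in Day 21 counts also rests on a lower limit taken from Phase 1 text.

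The size of any excess in event counts cannot be derived from the documents.

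**What to change.** 1. Reconcile Protocol 14.1, Table 4 footnote i and SAP 11, so that one sentence states when AE collection ended in each arm and whether 30 days was a minimum or a stop.
2. In SAP 11.2 and 19 and Protocol 16.5.2.3, cut every between-arm AE and SAE table at the same RT-anchored day. Either use 2 weeks after RT, already in the plan, or last RT/TMZ + 30 days. The later cut keeps more data, but it cannot be assumed that every Arm A patient was followed that far. Flag Arm A patients whose collection ended before the chosen cut and report observed days by arm.
3. Report Arm A events after the cut, to 30 days after the last BMX-001 dose, in a separate Arm A-only table.
4. Restrict any between-arm adjuvant table to the common window and label it as partial, or drop it. A cut at RT + 2 weeks would hold no adjuvant days under the assumed start, so this table would then go.

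The cost is SAP and protocol wording, a date filter and a flag. The downside is that late Arm A events move to a single-arm table. A common cut also does not equalise visits: Arm B has no Week 7 or 8 study visit, so detection may differ even inside the shared window, and a table footnote should say so.

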### 14.1.1 Reporting of AEs

BioMimetix JV, LLC should be notified of all treatment-related adverse events on a regular basis (to be agreed upon by the study team and BioMimetix JV, LLC).

## 14.2 Serious Adverse Events

An AE is considered "serious" if in the opinion of the investigator it is one of the following outcomes: - Fatal

- Life-threatening
- Constitutes a congenital anomaly or birth defect
- A medically significant condition (defined as an event that compromises subject safety or may require medical or surgical intervention to prevent one of the three outcomes above).
- Requires inpatient hospitalization or prolongation of existing hospitalization
- Results in persistent or significant incapacity or substantial disruption to conduct normal life functions.

#### 14.2.1 Reporting of SAEs

Only adverse events that the Sponsor and/or Principal Investigator determines to be serious, unanticipated, and related or possibly/probably (i.e., more likely than not) related to the research must be reported to the sponsor. Those adverse events will be submitted, according the following guidelines:

- Report within 24 hours of learning about any subject's death that was unanticipated and more likely related to the research than unrelated;
- Report within 5 business days of learning about any serious, unanticipated, and related or possibly/probably related adverse event; or other unanticipated problem or event that was more likely related to the research than unrelated.
- Report within 10 business days of learning about any other SAE not meeting the above criteria.

Refer to sponsor Standard Operating Procedures for SAE Reporting specifics.

The Principal Investigator is responsible for compliance with all applicable regulations pertaining to the reporting of adverse events to the IRB. Follow-up information on these events shall also be reported to BioMimetix JV, LLC, and the IRB as required as soon as follow up information is available. Follow-up information may include hospital admission records, discharge summaries and autopsy reports, where applicable.

The Sponsor must report to the FDA, in an IND safety report, any suspected adverse reaction that is both serious and unexpected. Before submitting this report, the sponsor needs to ensure that the event meets all three of the definitions contained in the requirement:

- Suspected adverse reaction (i.e. there is a reasonable possibility that the drug caused the adverse event)
- Serious
- Unexpected

If the adverse event does not meet all three of the definitions, it should not be submitted as an expedited IND safety report.

The Sponsor is required to report to the FDA all IND Safety reports in writing within 15 days (7 days for unexpected fatal or life-threatening suspected adverse reaction). The FDA Form 3500A can be found on the FDA website, www.fda.gov. All other adverse events will be reported to the FDA in the IND Annual Report.

In addition to the above mentioned reporting responsibilities, after discontinuation of the study, all SAEs considered to be drug related will be reported to BioMimetix JV, LLC, by the Principal Investigator.

## 14.3 External Data and Safety Monitoring Board (DSMB)

The DSMB-Plus established for Phase 1 will be used for Phase 2 during the period that Duke Cancer Center is the only participating clinical center. When additional clinical centers are added to the Phase 2 study, the DSMB-Plus will be modified to become a DSMB-Plus which has oversight for all clinical centers. This will involve approval of a new charter.

The sponsor and Principal Investigators are responsible for overseeing the safety and efficacy of the trial, executing the DSMB plan, and complying with all reporting requirements to local and federal authorities. Additional oversight will be carried out by an external DSMB In Phase 2.

An external DSMB-Plus will be utilized to monitor Phase 2 when this becomes a multi-center study. This DSMB will be organized to meet requirements of Western IRB, the institutional IRBs, and the NCI. We anticipate a charter with a minimum of 3 members, which may include: a radiation oncologist with experience in high grade glioma, a medical oncologist with expertise in high grade glioma, a biostatistician, and/or an ethicist or patient advocate. The responsibilities of the DSMB will be to review safety of study procedures, to maintain study integrity, to review adverse events and to review efficacy of the outcome data. The DSMB will meet either face to face or by teleconference or with electronic communication at least semi-annually and on an ad hoc basis as indicated by any adverse events. Minutes will be kept of both open and closed meetings of the DSMB. At the end of the study, all minutes taken will be available to the clinical trial principal investigators, the NCI, and BioMimetix JV, LLC.

The DSMB's responsibilities will include evaluation of treatment outcome for evidence of tumor protection by the study drug. The DSMB will have authority to recommend closure of the clinical trial for either efficacy or futility.

# **15 QUALITY CONTROL AND QUALITY ASSURANCE**

## 15.1 Monitoring

BioMimetix JV, LLC personnel will monitor this study. The Clinical Center Principal Investigator and Study Coordinator should be available to the clinical trial monitor during monitoring visits and ensure that access to all documents and records is provided. This local Principal Investigator agrees to cooperate with the clinical trial monitor to ensure that any problems detected in the course of these monitoring visits are resolved. For this study, the expected average monitoring frequency is at least one visit approximately every 10 weeks, while the study is enrolling and subjects are receiving treatment.

Additional monitoring may be prompted by findings from monitoring visits, unexpected frequency of serious and/or unexpected toxicities, or other concerns and may be initiated upon request of the clinical center institution, the Sponsor, the Clinical Center Principal Investigator, or the IRB. All study documents must be made available upon request to the clinical trial monitor and other authorized regulatory authorities, including but not limited to the National Institute of Health, National Cancer Institute, and the FDA. Every reasonable effort will be made to maintain confidentiality during study monitoring.

#### 15.1.1 DSMB-Plus

Per the recommendation of the Duke School of Medicine Research Integrity Office (RIO), a data safety monitoring board DSMB-Plus has been formed and a charter has been established for periodic review and assessment of data and outcomes to assure continuing safety of research participants in this trial. The committee will participate in decisions regarding reports or publications to ensure there is no bias as a result of conflict of interest questions. Because of Duke University's potential for conflict of interest with BMX-001, the Duke RIO has recommended use of a DSMB-Plus for review of the study for bias in the protocol design, performance of the study, and assessment of endpoints and ongoing periodic assessment of adverse events and study conduct.

Members of the DSMB-Plus will be approved by the ROI office and a DSMB-Plus charter established. For Phase 1 narrative summaries will be prepared by the study coordinator or research nurse and reviewed and signed by the PI. Of note, this DSMB-Plus will be involved in the Phase 1 portion of this study. Narrative summaries of subjects from each dose level will be prepared four weeks after the last dose of BMX-001. These summaries will include a review of safety data, Adverse Event assessments with attention paid to endpoint assessments and data in the protocol. PK data may also be reviewed at this timepoint. The DSMB-Plus committee will review narrative summaries and offer a recommendation about dose escalation or discontinuation of enrollment to the PI. Policies of the DSMB-Plus will be described in the DSMB-Plus Charter, which will be signed by the DSMB-Plus members and PI.

In Phase 1 DSMB-Plus meetings will be convened after the 3rd subject on a cohort (dose level) has reached 4 weeks after the last dose of BMX-001. DSMB-Plus review will be prior to each dose escalation. In Phase 2, the DSMB-Plus will meet twice a year. The DSMB-Plus will review safety and data reports which will be provided by the sponsor prior to the meetings. Review of data can be via WEBEX or teleconference. Copies of DSMB-Plus meeting minutes will be provided to RIO office ([name]) within 30 days of the DSMB-Plus review.

This DSMB-Plus committee will also consider conflict of interest questions related to this research. The DSMB-Plus will evaluate whether financially-linked biases have affected the design, conduct, or reporting of the research related to BMX-001. Policies of the DSMB-Plus will be described in the DSMB-Plus Charter, and signed by the DSMB-Plus members.

